The first objective (**Intervention 1**) will be achieved by comparing whole-body heat storage (measured using combined direct and indirect calorimetry) and the accompanying changes in body temperature (i.e., rectal, mean skin temperature), cardiovascular, and circulating and intracellular inflammatory and stress responses between young and older adults during a 9-hour resting exposure to ~40°C and ~10-15% relative humidity conditions (heat index: 37-38°C). These conditions were chosen to simulate peak temperatures experienced during heatwaves and are similar to conditions in recent heatwaves in North America in 2018 (Ottawa, Ontario; 34°C and 58%, heat index: 41°C) and Europe in 2003 (Paris, France; 38°C and 25%, heat index: 38°C). This intervention will thereby allow for the determination of whether ecologically valid heatwave conditions exceed the physiological capacity for heat dissipation in older adults, and how thermal and cardiovascular strain and inflammation develops during long-duration heat exposure.

The second objective (**Intervention 2**) will be accomplished by comparing physiological responses in the older adults in Intervention 1 to a separate age-matched group removed from the heat to spend 2 hours in a cooler environment (23°C, ~50% relative humidity) approximately mid-way (hours 5-6) through the simulated heatwave. Comparing whole-body heat storage and body temperature, cardiovascular, and inflammatory responses during and after the ambient cooling intervention to the non-cooled group will allow for determination of whether short-term cooling confers prolonged reductions in physiological strain or if the cooling-induced physiological alterations occur only transiently.

Hypotheses

Intervention 1: Age-related attenuation of the human heat loss responses (cutaneous vasodilation and sweating) means that older adults experience greater elevations in body heat storage and body core temperature compared to younger individuals during heat stress. For example, Kenny et al. (*Temperature (Austin)*. 2016 31;4(1):79-88). observed ~80% greater heat storage (equivalent to a ~0.5°C greater elevation in mean body temperature) in middle-aged-to-older compared to young adults during 3-hours of resting heat exposure. More importantly, the middle-aged-to-older adults did not achieve a state of heat balance (i.e., they were still storing heat within their body at the end of the 3 hours).

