2018 (Ottawa, Ontario; 34°C and 58%, heat index: 41°C) and Europe in 2003 (Paris, France; 38°C and 25%, heat index: 38°C). The participant will sit quietly for 3-hours (hours 1-3) within the calorimeter chamber while whole-body heat exchange is measured. Metabolic heat production will be evaluated simultaneously via indirect calorimetry (AMETEK model S-3A/1 and CD 3A, Applied Electrochemistry, Bastrop, TX, USA). At the 3-hour mark, participants will exit the calorimeter, and the brief cardiovascular test battery will be performed again, followed by a measurement of body mass.

Hours 4-6 will be spent resting in the heat in the thermal chamber (but outside of the calorimeter). During this time, the participant will be allowed to consume a light (~300 g), self-provided lunch with low water content (e.g., peanut butter sandwich). Tap water will be available *ad libitum* via a self-service insulated water cooler located in the thermal chamber (out of direct sight). Another cardiovascular battery will be performed followed by a measurement of body mass at the end of this period. The participant will then be transferred to the calorimeter where the final 3 hours will be spent resting in the seated position (hours 6-9). At the 9-hour time point, the participant will be removed from the calorimeter, the cardiovascular test battery was conducted, and a venous blood sample and body mass measurement will be procured. The participant will then be provided with water and/or a commercially available sports drink before leaving the laboratory.

Intervention 2: Efficacy of a cooling centre intervention for limiting physiological strain in the elderly

The protocol for Intervention 2 will be identical to that of Intervention 1 except that after the first calorimeter session and the subsequent cardiovascular battery, the participant will be removed from the thermal chamber to spend 2 hours (hours 5-6) seated in an air-conditioned room (~23°C, ~50% relative humidity). Like protocol 1, the participant will be able to consume water (tap) *ad libitum* and eat a small self-provided during this time. The third cardiovascular battery will be performed in the cooled environment. At the end of the 6th hour, participants will re-enter the calorimeter where they will spend the remaining 3 hours of exposure seated in the heat.

Measurements

Primary Outcome measures

Whole-body heat storage and body core temperature

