a sampling rate of 175 Hz). Normal-to-normal beats, as determined by the Zymed annotation algorithm, will be retained for further analysis. Continuous Individualized Variability Analysis (CIMVA) software (<http://ohridal.org/cimva/CIMVA-CoreDescription.pdf>) will be used to derive absolute heart rate and indices of heart rate variability (5 min windowed analysis with 30 sec time step). The latter includes 1) standard deviation of successive normal-to-normal intervals (SDNN), an index of overall variability; and 2) the root mean squared of the standard deviation (RMSSD) of successive normal-to-normal intervals, which is more reflective of short-term high frequency fluctuations in heart rate (mediated primarily by the parasympathetic nervous system).

Arterial systolic and diastolic blood pressures will be intermittently taken as an average of the three values measured at the brachial artery (~30 s between measures) via manual auscultation. Mean arterial pressure will be calculated as $2/3$ diastolic pressure + $1/3$ systolic pressure. Rate pressure product, an index of myocardial work, will also be derived as heart rate \times systolic pressure.

Brachial arterial blood pressures and cardiac output will be estimated from beat-to-beat recordings of arterial pressure waveform measured at the right middle-finger using the volume-clamp technique (Finometer Pro, Fina-press Medical Systems). Stroke volume will be calculated as cardiac output \div heart rate, whilst total peripheral resistance is derived as mean arterial pressure \div cardiac output. Cardiac baroreflex sensitivity will be determined via the sequence technique using software provided by Finapres Medical Systems (PRVBRS, Fina-press Medical Systems). Forearm and calf blood flows will be determined as the average of a minimum of four measurements obtained via automated venous occlusion plethysmography (Hokanson AI6, D.E. Hokanson, Inc.).

Circulating and intracellular inflammation and stress markers

Venous blood will be collected for the determination of circulating and intracellular inflammation/stress responses. Samples collected from the antecubital vein at baseline and the end of exposure will be transferred directly into Vacutainer tubes with no additive (1 x 5 mL SST™ Serum Separator Tube, BD) or potassium ethylenediaminetetraacetic acid (1 x 3 mL and 3 x 10 mL K₂EDTA [7.2 mg and 18 mg, respectively], BD).

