Statistical analysis for **Intervention 1** will compare whole-body heat storage and the resultant progression of body temperature, cardiovascular and acute inflammatory responses between the young and older adults during the simulated heatwave. Whole-body heat storage (primary outcome), body temperature responses including rectal temperature (primary outcome) and mean skin temperature (secondary outcome), as well as cardiovascular responses (secondary outcomes) will be evaluated using linear mixed-effects models. Time will be modelled as a repeated within-subject fixed effect (two levels: 3 and 9 hours), and age-group (two levels: young and older adults) will be modelled as a between-subject fixed effect. Pre-heat exposure values of the outcome variable, participant sex, and self-reported weekly physical activity (min/week, as assessed via the GAQ) will be included as covariates. Circulating and intracellular markers of acute inflammation and stress (secondary outcomes) will be evaluated using a similar model but without the fixed effect of time (data was only collected at the end of exposure) and baseline values included as a covariate (where appropriate). Participant identification will be modeled as a random effect in all analyses. Akaike's information criterion will be used to determine random effect and variance/covariance structures.

Post hoc multiple comparisons will be made on model estimated marginal means. Given the small number of comparisons for each variable, multiplicity corrections will not be employed. Homoscedasticity will be evaluated for all models by visual assessment of residual plots. Approximate normal distribution of residuals will be assessed via visual inspection of histograms and Q-Q plots. Data will be log-transformed in the event that the distribution of residuals meaningfully deviates from normality. For all analyses, the level of significance will be set at $P < 0.050$. Descriptive statistics will be presented as means and standard deviations. Comparisons between groups and/or time-points will be presented as means and 95% confidence intervals [lower limit, upper limit].

Intervention 2

Statistical analysis for Intervention 2 will evaluate the acute and lasting impacts of the short-term cooling intervention (i.e., during cooling and following return to the heat, respectively) on physiological responses.

Cumulative heat storage (primary outcome)

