The effect of the cooling intervention on cumulative whole-body heat storage over the 3 hours following return to the heat will be evaluated using a linear mixed-effects model with experimental group (two levels: cooling and no-cooling) modelled as a between-subject fixed effect. Cumulative heat storage over the first three hours of the 9-hour exposure will be included as a covariate to account for the influence of any inter- or intra-individual factors (e.g., sex, physical activity levels), measured or unmeasured, impacting whole-body heat exchange and storage. Comparisons of heat storage between groups will be made using model estimated marginal means.

Body core temperature (primary outcome)

Body core temperature, as estimated by rectal temperature, will be analyzed with a linear mixed effects model with experimental group (two levels: cooling and no-cooling) modelled as a between-subject fixed effect and time as a repeated within-subject fixed effect (0-, 1-, 2-, and 3-hours post-cooling intervention). Like the model for heat storage, rectal temperature at the end of the first calorimetry session (i.e., hour 3 of the 9-hour exposure) will be included as a covariate to account for the influence of any measured or unmeasured inter- or intra-individual factors impacting the body temperature responses to resting heat exposure.

Because this study was designed to assess the hypothesis that body core temperature will be similar (equivalent) between groups following return to the heat, the effect of cooling on rectal temperature will be assessed via two one-sided tests (see Lakens. *Soc Psychol Personal Sci.* 2017:8 (4), 355-362) performed on the mixed-effects model derived estimated marginal means at each timepoint. For the equivalence testing, the null hypothesis is taken as a meaningful difference between groups and its rejection therefore

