corresponds to an equivalence of means. These are presented alongside the results of a traditional Welch's t-test. This permits evaluation of both statistical differences, and statistical equivalencies in physiological responses. Performing analysis on the marginal means will allow for isolation of the effect of cooling from individual differences in the body temperature response to heat exposure (captured in the 3-hour timepoint covariate). Equivalence bounds will be set to $\pm 0.3^{\circ}\text{C}$, which corresponds to the typical day-to-day variation of core temperature (Consolazio et al. *Physiological measurements of metabolic functions in man*. 1963:453-480) and has been suggested to reflect a meaningful/detectable change in body temperatures in a recent study assessing the influence of cooling strategies on physiological strain in young adults (Morris et al. *Annals of Internal Medicine*. 2019;171(9):675-677).

Secondary outcomes

Mean skin temperature as well as cardiovascular responses and circulating/intracellular inflammatory/stress markers will be modeled with linear mixed-effects models. The analyses for mean skin temperature and cardiovascular responses will be performed similar to that for rectal temperature except only two time points will be included (0- and 3-hours post-cooling intervention). Circulating and intracellular changes in inflammatory markers, measured at the start and end of exposure only, will be analyzed with a linear mixed-effects model with age-group (two levels: young and older adults) modelled as a between-subject fixed effect, and participant sex, self-reported and weekly physical activity (min/week, as assessed via the GAQ), included as covariates.

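### The Intervention 2 inflammatory and stress-marker model omits the participant's baseline marker as a covariate and, as written, contains no cooling contrast

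*Combined protocol and SAP*

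**What the plan says.** The marker model is in the Statistical analysis plan, Intervention 2, Secondary outcomes. The outcome is described as "Circulating and intracellular changes in inflammatory markers, measured at the start and end of exposure only", and how a change is formed is not defined. The group term is given as "with age-group (two levels: young and older adults) modelled as a between-subject fixed effect". The covariates are "participant sex, self-reported and weekly physical activity (min/week, as assessed via the GAQ), included as covariates".

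The baseline value exists. The Measurements section on circulating and intracellular markers has "Samples collected from the antecubital vein at baseline and the end of exposure". The Experimental Design says "The protocol for Intervention 2 will be identical to that of Intervention 1 except that" the cooled participants leave the heat for two hours, so the cooling cohort also gives a baseline sample.

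Elsewhere the plan does adjust for a participant's own earlier value. For these same markers in Intervention 1 the text has "baseline values included as a covariate (where appropriate"). For Intervention 2 core temperature, "rectal temperature at the end of the first calorimetry session (i.e., hour 3 of the 9-hour exposure) will be included as a covariate". Heat storage is adjusted for storage over the first three hours, and skin temperature and cardiovascular outcomes follow the rectal-temperature approach.

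The comparison is between the older adults of Intervention 1 and a "separate age-matched group removed from the heat to spend 2 hours in a cooler environment". Participants gives 20 per group, and no randomisation between these groups is described.

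**The concern.** The marker model is the one Intervention 2 analysis that adjusts for no earlier value of the same outcome, and no reason is given. The omission matters because the Hypotheses section makes a claim that rests on this model: that any effect of cooling on acute inflammation has gone by the end of the heat event. A noisier contrast is less likely to reach significance, and here a non-significant result would look like agreement with the hypothesis. The noise also makes the exploratory equivalence tests harder to pass. With 20 per group, a chance difference in resting marker levels would pass in part into the estimate.

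The group factor is the more basic fault. Both groups in the Intervention 2 comparison are older adults, so a young/older factor does not separate them. The sentence reads as text carried over from Intervention 1, and the missing baseline term may be part of the same slip.

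**Working it through.** **The plan's own figure.** No power or sample size is stated for the markers. The only Intervention 2 figure is 18 per group for rectal-temperature equivalence (bounds ±0.3°C, SD 0.3°C, 80% power, one-sided 0.05). With a true difference of zero, n = 2 × [0.3 × (1.645 + 1.282) / 0.3]² = 17.13, rounded up to 18; the t-based power at 18 is 80.4%. It reproduces and does not depend on the marker model.

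**Inputs for the markers.** n = 20 per group (Participants). The documents give no marker SD and no baseline-to-end correlation, so r is assumed over 0.3 to 0.9, with equal SDs at both times. Results are in SD units.

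**Formulas.**
- Variance of a change score: 2(1 − r).
- Residual variance with baseline as covariate: 1 − r².
- Ratio: (1 − r²) / [2(1 − r)] = (1 + r)/2. The confidence interval narrows by 1 − √ratio.
- Difference detectable with 80% power at two-sided 0.05: (1.960 + 0.842) × √(2 × variance / 20).
- Expected shift of a change-score contrast for a chance baseline gap D: −(1 − r)D, shown for D = 0.5.

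| r | Change-score variance | Adjusted variance | Ratio | CI narrower by | Detectable difference, change → adjusted | Shift of change score, D = 0.5 |
|---|---|---|---|---|---|---|
| 0.3 | 1.40 | 0.91 | 0.65 | 19% | 1.05 → 0.85 | −0.35 |
| 0.5 | 1.00 | 0.75 | 0.75 | 13% | 0.89 → 0.77 | −0.25 |
| 0.7 | 0.60 | 0.51 | 0.85 | 8% | 0.69 → 0.63 | −0.15 |
| 0.9 | 0.20 | 0.19 | 0.95 | 3% | 0.40 → 0.39 | −0.05 |

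These ratios ignore the cost of estimating the slope. With chance imbalance only and normally distributed baselines, that cost multiplies the adjusted variance by about 1 + 1/(2 × 20 − 4) = 1.028. At r = 0.9 the ratio becomes 0.95 × 1.028 = 0.98, so the gain there is close to nil.

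**Likely size of a chance gap.** Its SD is √(2/20) = 0.32, with a 95% range of ±1.96 × 0.32 = ±0.62, so a gap of 0.5 is within ordinary chance.

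**If the end value alone were modelled.** The variance is 1, so adjustment leaves 1 − r² of it: 0.91, 0.75, 0.51 and 0.19 for the same r. A chance gap of 0.5 shifts the unadjusted contrast by +0.5r: 0.15, 0.25, 0.35 and 0.45. The word used for the outcome points away from this reading.

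**If the gap is systematic.** Suppose recruitment gives the cohorts means that stay D apart and cooling has no effect. The change-score contrast then has expectation D − D = 0, while the adjusted contrast has expectation D − rD = (1 − r)D. At D = 0.5 that is +0.35 to +0.05 over r = 0.3 to 0.9: the same size as the table's last column, but now in the adjusted estimate (Lord's paradox).

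**The case against.** The strongest objection is the last calculation. A reader might infer that the planned change score is biased by any baseline difference between the cohorts, and that adjustment cures it. The documents do not support that. The −(1 − r)D shift applies to a chance gap and assumes equal variances. The cohorts are recruited separately, and for a stable gap it is the adjusted estimate that moves. This stands, and it is why both models should be reported.

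Second, a reader might infer that baseline is ignored altogether. The outcome is described as changes, so baseline probably enters through the outcome. What is missing is baseline as a covariate.

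Third, the consistency argument has limits. The other Intervention 2 covariates are responses over the first three hours of heat. No blood is drawn at hour 3, so that rule cannot be copied to the markers; the pre-exposure sample is the only earlier value. The Intervention 1 sentence is also loosely worded: it is qualified, it could be read as excluding baseline, and its remark that data come only from the end of exposure conflicts with the Measurements section. Including baseline is its natural reading, not its only one.

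Fourth, the plan describes participants as homogeneous, age-matched and relatively healthy, which may limit imbalance. That does not remove chance variation at 20 per group, or the loss of precision.

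**Conclusion.** The point holds for these secondary outcomes. The marker sentence omits an already collected baseline covariate and names the wrong group factor. Against a change score, adjustment leaves 0.65 to 0.95 of the residual variance, so intervals are 19% to 3% narrower before the small cost of estimating the slope. That range rests on an assumed r of 0.3 to 0.9 and equal variances. Adjustment also removes the effect of chance imbalance, but not confounding between non-randomised cohorts.

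Three further inferences go too far. The marker results of the two interventions are not made non-comparable by this: they answer different questions, and other outcomes already use different covariates by design. The documents do not show that a log scale is required or that the Intervention 1 qualifier must be deleted; those are matters of preference. And the missing cooling term is confined to the marker sentence: the heat-storage and rectal-temperature models name cooling and no-cooling explicitly.

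**What to change.** Rewrite the marker sentence under Intervention 2, Secondary outcomes, in one edit:

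- Outcome: the end-of-exposure marker, using plasma-volume-corrected values for the serum markers.
- Between-subject factor: experimental group, cooling or no-cooling.
- Covariates: the participant's baseline value of the same marker, sex, and weekly physical activity.
- Sensitivity analysis: the change from baseline with the same factor, sex and activity, reported beside the main result because the cohorts are not randomised. If the two disagree, say so and do not attribute the difference to cooling.

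The plan states that it was submitted after the data were cleaned and analysed but before unblinding, so the edit should be dated and labelled as a change to the plan.

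The cost is one degree of freedom and a rerun of the secondary marker models. No new samples are needed.

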Based on this work, our primary hypothesis is that older adults will not achieve a state of heat balance (i.e., rate of heat loss balancing the rate of heat gain; thermal equilibrium) and therefore experience greater heat storage throughout the 9-hour simulated heatwave compared to the younger participants. Consequently, body core temperature will be greater in the older adults and between-group differences will be exacerbated as exposure progresses. We will also explore the secondary hypothesis that differences in body temperature will be paralleled by greater alterations in cardiovascular variables and circulatory and intracellular markers of acute inflammation and stress in the older adults.

Intervention 2: Our primary hypothesis is that body heat storage will be exacerbated in the older adults exposed to the cooling centre intervention upon return to the heat (hours 5-6) compared to the older adults from Intervention 1 who remained in the heat. Consequently, body core temperature will be comparable (statistically equivalent) between groups by the end of exposure (i.e., 9 hours, 3 hours after return to the heat). This is because body temperature is regulated through a negative feedback mechanism. Elevations in core and skin temperatures elicit proportional activation of cutaneous vasodilation and sweating to facilitate heat loss and stabilize body temperature. Thus, core and skin cooling will suppress heat loss and, upon return to a hot environment, heat will be rapidly gained until body temperature rises to an extent sufficient to activate heat loss and re-attain thermal equilibrium. We will also evaluate the secondary hypothesis

that, in parallel to body core temperature, any effect of cooling on cardiovascular responses and acute inflammation will be abated by the end of the heat event.

METHODS

Participants

A total of 20 young (age: 18-30 years) and 40 older (age: 64-80 years) adults will be recruited for the project. Young (n=20) and older (n=20) adults will be recruited for **Intervention 1** and a separate cohort of older adults (n=20) for **Intervention 2**. Details on the determination of the sample sizes for each intervention are provided below.

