Intervention 1: An *a priori* power analysis determined that a total sample size of 19 young and 19 older adults is required to detect a difference in the rate of whole-body heat storage between groups at the end of each calorimeter session (i.e., hours 3 and 9) with 80% statistical power. In lieu of clinically meaningful data (i.e., what would be considered a clinically meaningful change in whole-body heat storage), the standardized effect size (Cohen's $d = 1.06$) was calculated from the difference in the rate of body heat storage between young and older adults over the final 30-min of a 3-hour heat exposure (young: -2 [26] kJ/hour, older: 43 [54] kJ/hour) in our previous work (Kenny et al. *Temperature (Austin)*. 2016 31;4(1):79-88).

Intervention 2: An *a priori* power analysis determined that a total sample size of 18 older adults in each group is required to confirm whether between-group differences in rectal temperature are within upper and lower bounds of +0.3°C and -0.3°C, respectively, with 80% power. This corresponds to an effect size (Cohen's d) of 1.0, based on the pooled-standard deviation of 0.3°C. Equivalence bounds were chosen based on the typical day-to-day variation of body core temperature (Consolazio et al. *Physiological measurements of metabolic functions in man*. 1963:453-480) and suggested meaningful/detectable change in body core temperature in a recent study assessing the influence of personal cooling strategies on physiological strain in young adults (Morris et al. *Annals of Internal Medicine*. 2019;171(9):675-677). The standard deviation for the between group difference was determined from data from our laboratory demonstrating a 0.2°C (SD 0.3) difference in rectal temperature between young and older adults (Kenny et al.

Temperature (Austin). 2016;4(1):79-88) and a 0.0°C (SD 0.3) difference between older adults with and without type 2 diabetes (Poirier et al. *Temperature (Austin)*. 2020;7(3):263-269) during 3 hours of rest in the heat (44°C, 30% relative humidity).

Experimental Design

Pre-trial instructions

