The analysis of secondary variables will focus on whether there was a lasting effect of cooling 3 hours following return to the heat. However, we will also perform tertiary exploratory analysis to evaluate whether the end-exposure responses are similar (equivalent) within pre-specified bounds. Describing clinically meaningful bounds in this context is complex since there is little research regarding how the risk of adverse health events changes with *acute* alterations in cardiovascular responses or inflammatory status during heat exposure (or cooling). For heart rate (± 5 beats/min) and rate pressure product (± 1500 beats/min), the equivalence bounds for these exploratory analyses will be based on meaningful/detectable differences employed in recent studies evaluating the efficacy

of personal cooling strategies in laboratory-based studies (Morris et al. *Annals of Internal Medicine*. 2019;171(9):675-677). For arterial blood pressure responses, we will consider ± 5 mm Hg an appropriate clinically meaningful bound, given the associated 9%, 13%, and 6% reduction in risk of myocardial infarction, stroke, and mortality (Psaty et al. *Arch Intern Med*. 2001;161(9):1183-1192). For the other variables, reasonable equivalence bounds are not forthcoming. We will therefore set the bounds for these outcomes at ± 1 SD of the between-group difference (based on our sample size determination).

For all models, participant identification will be modeled as a random effect and Akaike's information criterion will be used to determine random effects and variance/covariance structure. The level of significance will be set at $P < 0.050$. Descriptive statistics will be presented as mean (standard deviation). Both 90% confidence intervals and 95% confidence intervals will be computed to facilitate interpretation of the equivalence testing and null hypothesis significance testing (respectively).

As noted at the start of the document, the statistical analysis plan was submitted after cleaning and analysis of the full data set, but prior to unblinding of the data.

Delimitations and limitations

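### Intervention 2 predicts that cooling effects have abated by hour 9, but ranks the equivalence test of that prediction as tertiary and gives no rule for reading a non-significant difference

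*Combined protocol and SAP*

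**What the plan says.** The Hypotheses section, under Intervention 2, predicts in parallel with core temperature that "any effect of cooling on cardiovascular responses and acute inflammation will be abated by the end of the heat event". This is a prediction of no remaining effect.

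The SAP for Intervention 2 treats two hypotheses of this form differently:

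- **Rectal temperature (primary).** Because the hypothesis is one of similarity, the SAP specifies two one-sided tests with bounds of ±0.3°C on the model's marginal means, shown beside a conventional difference test.
- **Secondary outcomes.** "The analysis of secondary variables will focus on whether there was a lasting effect of cooling 3 hours following return to the heat". The SAP then adds a "tertiary exploratory analysis to evaluate whether the end-exposure responses are similar (equivalent) within pre-specified bounds". The bounds are ±5 beats/min for heart rate, ±1500 for rate pressure product, ±5 mm Hg for arterial pressures, and ±1 SD for the remaining outcomes, for which it says no reasonable bound is available.

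On modelling, skin temperature and cardiovascular outcomes follow the rectal temperature approach, limited to the end of cooling and 3 hours later. The SAP plans 90% intervals for equivalence and 95% intervals for difference testing. The inflammatory marker model is described separately, with age-group (young, older) as its between-subject factor.

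**The concern.** A difference test takes no effect as its null hypothesis, so failing to reject it does not show that an effect has gone. The SAP applies this logic to rectal temperature and then reverses the ranking for the parallel secondary hypothesis. There the difference question comes first, and the only test that can support abatement is placed below it. No sentence says what a non-significant difference would mean.

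The study asks whether benefit from a cooling centre lasts. If a non-significant result were reported as abatement, the trial could state that no cardiovascular benefit remained merely because 20 per group is too few to detect a moderate one.

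**Working it through.** **Inputs from the documents.** 20 cooled and 20 non-cooled older adults; significance level 0.05, two-sided for difference tests (95% interval) and 0.05 per side for equivalence (90% interval); the bounds above. **Assumptions.** The documents give no SDs for secondary outcomes and no covariate correlations, so ranges are shown. No dropout allowance is applied.

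**1. The plan's own figure.** The sample size section says that "a total sample size of 18 older adults in each group is required". With margin 0.3°C, SD 0.3°C and true difference zero:

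n = 2 × [SD × (z₀.₉₅ + z₀.₉₀) / margin]² = 2 × (1.645 + 1.282)² = 17.13, rounded up to 18.

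Exact-t equivalence power is 80.5% at 18 per group. The figure reproduces, but it covers rectal temperature only. No calculation is given for the secondary outcomes.

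**2. Difference test at 20 per group.** There are 38 degrees of freedom, the critical t is 2.024, and the noncentrality is d × √(20/2) = 3.162d.

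- d = 0.5: noncentrality 1.581, power 33.8%, missed 66.2%.
- d = 0.7: noncentrality 2.214, power 57.8%, missed 42.2%.
- 80% power is reached only at d = 0.91.

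**3. With the hour-3 covariate.** If the covariate correlates r with the outcome, the effective d is d/√(1 − r²). For d = 0.5:

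- r = 0.5: effective d 0.577, missed 57%.
- r = 0.7: effective d 0.700, missed 42%.

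**4. A true effect at the plan's own bound.** Suppose a true 5-unit difference in heart rate or pressure remains. At assumed SDs of 8, 10 and 12, the unadjusted difference test is non-significant 51%, 66% and 75% of the time. An equivalence test with ±5 bounds would wrongly pass at most 5% of the time (3.8% at SD 8, 0.9% at SD 10).

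**5. What equivalence can deliver at 20 per group.** The half-width of the 90% interval is 1.686 × SD × √(2/20). Power is at true difference zero with ±5 bounds, unadjusted.

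| Assumed SD | Half-width | Power | n per group for 80% |
|---|---|---|---|
| 5 | 2.67 | 86% | 18 |
| 8 | 4.27 | 24% | 44 |
| 10 | 5.33 | 3% | 69 |

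Covariate adjustment replaces SD by SD × √(1 − r²). For SD 8 this gives 6.93 (r = 0.5) or 5.71 (r = 0.7), with power 45% or 72%. For SD 10 it gives 8.66 or 7.14, with power 14% or 40%. For rate pressure product with ±1500 bounds, unadjusted power is 86%, 51%, 18% and 3% at assumed SDs of 1500, 2000, 2500 and 3000.

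**6. The ±1 SD bounds.** At 20 per group, power is 86% at true difference zero, but a true 0.5 SD effect also passes 46% of the time. These bounds are tied to the sample size determination, not to clinical relevance, so passing them is weak evidence of abatement.

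**7. Inflammatory markers.** Both Intervention 2 groups consist of older adults. A model whose group factor is young versus older contains no cooling contrast, so as written it can neither support nor refute abatement.

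**The case against.** A reader might infer that the plan intends to count non-significance as proof of abatement, or that it omits equivalence testing for these outcomes. The documents support neither. No sentence gives such a decision rule. The SAP says that "we will also perform tertiary exploratory analysis to evaluate whether the end-exposure responses are similar (equivalent) within pre-specified bounds", and it plans 90% and 95% intervals, so both kinds of result should be visible. Modelling skin temperature and cardiovascular outcomes like rectal temperature could even be read as bringing in the two one-sided tests, although the later exploratory label leaves their status unclear.

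The SAP also gives a reason for its ranking: little research ties acute changes in these responses to risk, so bounds are hard to justify. That reason stands for the outcomes given ±1 SD. It is weaker for heart rate, rate pressure product and arterial pressures, where the SAP names a bound and a basis for it.

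The 66% figure ignores the hour-3 covariate and uses an effect size that the documents do not state. For outcomes with ±1 SD bounds, a 0.5 SD difference lies inside the plan's own margin, so by that standard declaring equivalence would not be an error. Both points limit the size of the problem. They do not supply the missing rule.

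**Conclusion.** The concern holds as a fault of ranking and of a missing decision rule. A stated secondary hypothesis of no remaining effect has the difference question as its main analysis, its suitable test is labelled tertiary, and nothing says that non-significance without equivalence is inconclusive. The plan does not itself commit the error; it leaves room for it.

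The room is considerable: a 0.5 SD lasting effect would be missed 66% of the time unadjusted, or 57% or 42% with the covariate at r = 0.5 or 0.7. The effect size and correlations are assumptions. These are secondary outcomes and the primary rectal temperature analysis is unaffected, so the change should be made but does not threaten the main result. For inflammatory markers no cooling conclusion is possible until the model's group factor is corrected.

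**What to change.** 1. For heart rate, rate pressure product and arterial pressures, name the planned equivalence test at 3 hours after cooling as the analysis of the secondary hypothesis. Conclude abatement only if the 90% interval lies wholly within the stated bound.
2. For outcomes without a justified bound, including those given ±1 SD, keep equivalence exploratory and report the estimate with its interval.
3. State for all secondary outcomes that a non-significant difference alone is inconclusive.
4. In the Intervention 2 inflammatory marker model, replace age-group with cooling group.

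Items 1 to 3 need no new data and no new kind of test. The price is in the conclusions: if SDs are near 8 to 10, heart rate and pressure results will often be inconclusive even when cooling leaves no effect (unadjusted power 24% to 3%). Because the SAP says it was submitted after analysis of the full data set but before unblinding, the change should be dated, with a statement of whether it was made before unblinding.
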